5.9.1 Post Treatment Methods and Procedures

A focused medical history will be obtained and recorded in the clinical record by the treating investigator or qualified designee, as well as any changes in concomitant medical conditions, current medications, allergies, or social history. Current symptoms will be elucidated and recorded in the clinical record.

5.9.2 Post Treatment Scales and Assessments

The treating investigator or qualified designee will take vital signs including temperature, pulse, respiratory rate, weight and blood pressure. The body mass index (BMI) and body surface area (BSA) will be calculated.

• The treating investigator or qualified designee will assess ECOG status (Appendix B) at each visit.

- A CT scan with intravenous contrast of the chest, abdomen, pelvis (as well as the neck if previously involved with disease) is recommended at the time of the end-of-treatment visit as a standard-of-care disease assessment at approximately 18 months following treatment initiation (6 months post treatment competition), but is not required per the study protocol.
- A blood sample is to be provided to the main University of Chicago site for circulating methylation profiling (see Section 5.10) at approximately 18 months following treatment initiation (6 months post treatment completion) and again at 30 months post treatment initiation (18 months post treatment completion).
- At 30 months post treatment initiation (18 months post treatment completion) PET imaging for disease response (secondary outcome assessment) must be completed. See Appendix E for details of PET interpretation and response assessment.

5.9.3 Post Treatment Examinations and Questionnaires

The treating investigator or qualified designee will perform a focused physical exam during each visit. Clinically significant abnormal findings should be recorded as medical history. The treating investigator or qualified designee may use standard intake forms to facilitate the collection of changes in medical history, and medication list. These must be verified in a face-to-face encounter. No additional questionnaires are required.

5.9.4 Post Treatment Laboratory Studies

At each post-treatment visit, the following studies should be obtained:

- Complete blood count (CBC) with differential counts including hemoglobin, hematocrit, red blood cell count, mean corpuscular volume, white blood cell count, platelet count, absolute and relative neutrophil count, absolute and relative lymphocyte count, absolute and relative monocyte count, and absolute and relative eosinophil count.
- Complete metabolic panel including serum glucose, sodium, potassium, chloride, bicarbonate, blood urea nitrogen, creatinine, total protein, albumin, alanine transaminase, aspartate transaminase, and alkaline phosphatase.
- Serum lactate dehydrogenase level.

5.10 SAMPLE SHIPPING INSTRUCTIONS

5.10.1 Tissue for Correlative and Central Pathology Review

Archival tissue from a diagnostic tumor biopsy should be obtained and sent to the University of Chicago Study Coordinator during the pre-screening phase of the trial. Please send all stained slides, as well as 10 to 20 formalin-fixed paraffin-embedded (FFPE) unstained slides of 4 to 5µm thickness and/or the paraffin-embedded tissue block, if available (see below). If 10 to 20 unstained FFPE slides are not available, please provide any number of slides that may be available. Please ensure that all slides are properly labeled and that appropriate inventory sheet (see Appendix I) is included in each shipment. Please ensure that each slide is labeled with the following information: subject initials, subject ID number, date of biopsy, and specify biopsy site if slides from different origins are being submitted.

Tissue blocks are preferred to unstained slides if available, and can also be submitted to the University of Chicago in order for sections to be cut. All tissue blocks will be returned to the originating institute as

instructed on the inventory sheet (Appendix I). A copy of the completed inventory sheet should be made and filed in the corresponding subject's study files. Please refer to Section 5.10.3 for more details on how processed samples should be shipped.

5.10.2 Blood Specimen Collection and Processing for Correlative Studies

The blood draw for the correlative studies will occur at the screening visit, cycle 4 day 1, cycle 6 day 1, end-of-treatment visit, 18 months after treatment initiation, and 30 months after treatment initiation (see Appendix A). At each time point, 20mL blood in lavender-top BD Vacutainer K2 EDTA tubes will be drawn. The blood specimen for plasma isolation should be processed on site *within 2 hours* from the time of collection according to the following protocol:

- Place the lavender-top tube on ice after draw and centrifuge within 1-2 hours
- Centrifuge at 4° C at 1000 x g for 15 minutes
- Remove the plasma supernatant and store at -80°C in 1-2 mL aliquots.
 - i) In order to avoid breakage during freezing or leaking during thaw for analysis, please do not overfill the aliquots.

Please ensure that each aliquot is labeled with the following information: subject initials, subject identification number, visit, and aliquot identifier (e.g. a, b, c, etc.). All correlative specimens that are processed on-site should be sent in batches every 2 to 3 months on dry ice via overnight to the University of Chicago. All shipments must be accompanied with the appropriate inventory sheet (Appendix J). A copy of the completed inventory sheet should be made and filed in the corresponding subject's study files. Please refer to Section 5.10.3 for more details on how processed samples should be shipped.

5.10.3 General Shipping Instructions

Please arrange all shipments so that they are sent out to the University of Chicago Monday through Thursday. No shipments should be sent out on Fridays or the day prior to a holiday as shipments cannot be received on weekends and/or holidays. Shipments should be packaged in accordance with the appropriate regulations as specified by the carrier.

Please ensure that all aliquots are properly labeled and that the appropriate inventory sheet (Appendix I or Appendix J) is included in each shipment. In order to alert the study team of an upcoming shipment, please email the details of the shipment to the University of Chicago Study Coordinator, at [contact]. The email should contain the completed inventory sheet, or if the sheet cannot be emailed it should be faxed to: [contact].

Shipment should be sent to the following address:

University of Chicago Medicine Attention: [name] [name] Business [contact] Business [contact]

6 STATISTICAL PLAN AND CONSIDERATIONS

6.1 SAMPLE SIZE DETERMINATION

The sample size of the dose-finding arm may vary based on the number of adverse events in the lower dose levels, with an estimated size of 12-18 subjects. The number of subjects for the expansion cohort was calculated using $\alpha = 0.1$, $\beta = 0.2$, power $(1 - \beta) = 0.8$, a dichotomous study outcome, null hypothesis (H0) proportion of 0.3, and an alternative hypothesis proportion of 0.5. Enrolling 32 patients in a Simon two-stage design yields an α of 0.0997, 1- $\beta = 0.8038$, and a probability of correctly stopping after 15 patients if the null hypothesis is true of 72.16%.

6.2 STATISTICAL METHODS

6.2.1 Dose Finding Cohort

A 3+3 trial design with 3 dose levels and 2 optional dose de-escalation levels will be used (see Section 4.2 for details). This rule-based design proceeds with cohorts of three patients; the first cohort is treated at a starting dose that is considered to be safe based on prior human studies, and the subsequent cohorts are treated at increasing dose levels that have been fixed in advance (Storer 1989). Safety and tolerability for the purpose of dose-finding for the three-drug combination will be assessed in the first 28-day cycle of therapy.

The definition of dose limiting toxicity (DLT) is as follows:

- Grade 3 or 4 treatment-related non-hematologic toxicity with the exceptions of fatigue, anorexia, nausea, and fever without neutropenia
- Grade 4 treatment-related hematologic toxicity (anemia, thrombocytopenia and/or neutropenia) either lasting > 7 days despite supportive care or complicated by hemorrhage
- Any grade 5 toxicity.

If none of the three patients in the first cohort experiences a DLT within a 28-day cycle, the dose level will be advanced to DL2. If one or more of the patients at a certain dose level experiences a dose-limiting toxicity, three more patients will be treated at the same dose level. If there are two or more DLTs in a cohort of 3-6 patients at dose level 1, three patients will be enrolled at DL-1. If there are two more DLTs at dose level -1, three patients will be enrolled at DL-2.

If the dose level has been advanced to level 2 already, and two or more patients in a cohort of 3-6 patients experience dose-limiting toxicity, the RP2D will be defined as dose level 1. If a dose level has been lowered to DL-1 or DL-2 and no patients experience a DLT, that dose will be the RP2D. If one patient in a cohort at DL-1 and DL-2 experiences a DLT, another three patients will be enrolled. If none of the subsequent cohort experience a DLT, the dose level will be taken as the RP2D.

If there are no DLTs at DL2, DL2 will be the RP2D.

NOTE: The RP2D will be determined based on an integrated evaluation of the efficacy, safety, and tolerability of all evaluated dosing cohorts.

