The study design consists of two arms. First, in the dose-finding arm aimed at establishing a recommended phase 2 dose and uncovering dose limiting toxicities in a novel triplet combination therapy, all three investigational agents will be given together starting in cycle 1. This will allow early assessment of toxicity from the three-drug combination and efficient progression through dose levels in a standard "3 + 3" design.

In the expansion cohort, a "window" design will be used to explore the efficacy of the combination of venetoclax and CC-486 alone before obinutuzumab is added in cycle 4. The efficacy of anti-CD20 therapy in FL is already well-established, and this design will provide an opportunity to assess the effects of a novel two-drug combination independent of confounding effects of an agent known to be effective for many patients. To minimize the chance of exposing patients to a futile treatment, the expansion cohort will follow a Simon two-stage design for an interim assessment of efficacy based on response to the three-drug combination at 6 months. The study will be halted for futility if the criteria for early efficacy are not met.

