2 STUDY DESIGN

2.1 TYPE OF STUDY

The study will consist of two sequential single arms. Patients meeting enrollment criteria will be assigned non-randomly to the study arms based on order of enrollment. Neither patients nor investigators will be blinded to the assignment. First, a dose finding arm with a standard "3 + 3" design will use venetoclax, CC-486, and obinutuzumab combination therapy in three dose levels and two optional dose de-escalation levels to establish the RP2D and assess toxicity and tolerability of the triplet. Dose-limiting toxicity will be assessed during the 28 days of Cycle 1. If a safe and tolerable RP2D is established, the study will proceed with an expansion cohort using Simon two-stage and window designs. In the expansion cohort, the first three cycles will consist of a combination of venetoclax and CC-486 before obinutuzumab is added in cycle 4. Disease assessment will take place after cycle 3 and cycle 6 and will be graded according to the Lugano Criteria (B. D. Cheson et al. 2014). Adverse events (AEs) will be monitored throughout the trial, and graded in severity according to the guidelines outlined in the NCI Common Terminology Criteria for Adverse Events (CTCAE) version 5.0. This trial will be conducted in accordance with Good Clinical Practices.

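### Section 6.2.1: DLTs in two or three of the first three patients meet both the refill rule and the stopping rule, and neither is given precedence

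*Combined protocol and SAP*

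**What the plan says.** All the operative rules are in 6.2.1 Dose Finding Cohort.

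- **Refill, any level, counted in patients:** "If one or more of the patients at a certain dose level experiences a dose-limiting toxicity, three more patients will be treated" at the same level.
- **DL1, counted in DLTs:** "If there are two or more DLTs in a cohort of 3-6 patients at dose level 1, three patients will be enrolled at DL-1".
- **DL-1, counted in DLTs:** "If there are two more DLTs at dose level -1, three patients will be enrolled at DL-2".
- **DL2, counted in patients:** once DL2 is reached, if "two or more patients in a cohort of 3-6 patients experience dose-limiting toxicity", the RP2D is DL1.
- **DL-1 and DL-2 refill, counted in patients:** "If one patient in a cohort at DL-1 and DL-2 experiences a DLT, another three patients will be enrolled".

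No rule says what follows two or more affected patients at DL-2 or DL3.

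Section 2.1 describes "a dose finding arm with a standard '3 + 3' design will use venetoclax" in combination with the other two drugs, and 1.1.7 expects "efficient progression through dose levels in a standard '3 + 3' design". Neither section sets out the rules of that design. Sections 2.5 (cohorts of three) and 4.2.1.1 (dose levels) add no order of precedence.

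**The concern.** These sentences decide whether the next three patients receive a dose. After two or three affected patients in the first three at DL1, one sentence says to treat three more there and another says to enrol at DL-1. At DL2, one says to treat three more and another fixes the RP2D at DL1. A site or coordinating team following either sentence departs from the other.

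What is at stake is avoidable exposure: three further patients on a new three-drug combination, at a dose that has already met its own limit.

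A smaller inconsistency sits in the same sentences. The DL1 and DL-1 thresholds count DLTs, while the refill and DL2 rules count patients. One patient with two separate qualifying toxicities would meet the DL1 threshold but would count once at DL2.

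**Working it through.** **Step 1. Set the rules against each first-cohort result (counted in patients).**

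| Affected of first 3 | Refill rule met? | Stopping rule at DL1 or DL2 met? |
|---|---|---|
| 0 | No | No |
| 1 | Yes | No |
| 2 or 3 | Yes | Yes |

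The last row is the conflict. At DL-1 the threshold is worded as two more DLTs. It may be a slip for two or more, or it may mean two further DLTs occurring at DL-1. On either reading, two affected patients of three at DL-1 meet both that threshold and the general refill rule.

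**Step 2. Inputs.** The plan states no operating characteristics for dose finding, so there is no figure to reproduce. It gives no DLT rate for the triplet, and 7.2 calls the toxicity risks unknown. The true per-patient rate p is therefore assumed to be 0.10, 0.20 or 0.30. Let X be the number affected among the first three, X ~ Bin(3, p).

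**Step 3. Formulas.**

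- Conflict: P(X ≥ 2) = 3p²(1−p) + p³
- Exactly one affected: P(X = 1) = 3p(1−p)²
- Further affected patients per literal refill: 3p
- Expected patients at the level, refill on exactly one: 3 + 3·P(X = 1)
- Expected patients at the level, refill on one or more: 3 + 3·P(X ≥ 1)
- Leaving the level: P(X ≥ 2) + P(X = 1)·[1 − (1−p)³]

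**Step 4. Results.**

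| | p = 0.10 | p = 0.20 | p = 0.30 |
|---|---|---|---|
| P(X ≥ 2) | 0.027 + 0.001 = 0.028 | 0.096 + 0.008 = 0.104 | 0.189 + 0.027 = 0.216 |
| P(X = 1) | 0.243 | 0.384 | 0.441 |
| Further affected per literal refill | 0.3 | 0.6 | 0.9 |
| Expected patients, refill on exactly one | 3.73 | 4.15 | 4.32 |
| Expected patients, refill on one or more | 3.81 | 4.46 | 4.97 |
| P(leave level), either reading | 0.028 + 0.243 × 0.271 = 0.094 | 0.104 + 0.384 × 0.488 = 0.291 | 0.216 + 0.441 × 0.657 = 0.506 |

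The last row is the same under both readings because two affected patients among three are still at least two among six. Averaged over all first cohorts, the extra affected patients number 3p·P(X ≥ 2) = 0.008, 0.062 and 0.194.

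**Step 5. Counting unit.** Let q be the share of patients with a DLT who have two qualifying events. The documents do not give q, so 0.05 to 0.20 is assumed. Counting events at DL1 adds P(X = 1)·q·(1−p)³ to the probability of de-escalating:

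- p = 0.10: 0.243 × 0.729 × q = 0.009 to 0.035
- p = 0.20: 0.384 × 0.512 × q = 0.010 to 0.039
- p = 0.30: 0.441 × 0.343 × q = 0.008 to 0.030

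**The case against.** The strongest reply is that the intended rule is plain. If refilling always came first, every level with two or more affected patients would hold six before anyone acted, and the lower bound of 3 in the 3-to-6 range would do no work. The stopping rules are specific to a level, while the refill rule is general. The design is called a standard 3+3, and the separate refill sentence for DL-1 and DL-2 says one patient. Section 10.1 adds weekly safety review.

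Most of this stands. It makes the standard rule a fair inference and is why the severity is moderate. It does not remove the conflict. No sentence sets precedence, the label comes without its rules, and weekly review does not say which sentence governs.

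It is also fair that low DLT rates have some support. Section 1.1.4 reports no DLTs in two CLL studies of venetoclax with obinutuzumab, nor in the FL cohort given venetoclax alone, and 1.2.2.1 expects none here. The triplet itself is untested, so the range up to 30% is kept as an assumption.

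A reader might infer two stronger points.

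- **That the overlap could carry a too-toxic dose forward.** It could not at DL1 or DL2, since the decision to leave the level is identical under both readings.
- **That counting DLTs instead of patients would by itself lower the RP2D.** The documents do not support this. The closing note in 6.2.1 bases the RP2D on an integrated evaluation across all dosing cohorts, and a threshold written over 3 to 6 patients is most naturally read per patient.

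**Conclusion.** The refill rule is wrong as written. At DL1, DL2 and DL-1 it overlaps the stopping rules for two or three affected patients in the first three, and nothing says which applies. At assumed true DLT rates of 10/20/30% this arises in 2.8/10.4/21.6% of first cohorts. Each literal refill then exposes three more patients, with 0.3/0.6/0.9 further affected patients expected. These figures describe the literal reading, not predicted conduct. They rest on assumed rates and on independent patients with a common rate.

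Severity is moderate: the harm is avoidable exposure, no decision to leave a level changes, and the intended rule can be inferred. The counting-unit mismatch is a minor consistency point, worth about 0.8 to 3.9 percentage points at DL1 over the same rates on an unsourced assumption about q.

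**What to change.** Reword four sentences in 6.2.1.

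1. **Refill:** treat three more patients at a level only if exactly one of the first three treated there has a DLT.
2. **DL1, DL-1 and DL2 thresholds:** state each as two or more patients with at least one DLT among the 3 to 6 treated at that level. This corrects the DL-1 wording and counts patients throughout. Keep the existing actions: DL1 to DL-1, DL-1 to DL-2, and at DL2 the RP2D is DL1.

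Add two sentences, because the general refill rule is now the only instruction for two or three affected patients at DL-2 and DL3, and narrowing it would leave a gap.

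3. **DL-2, the lowest level in Table 2:** two or more affected patients end dose finding with no RP2D. This agrees with the condition in 2.1: "If a safe and tolerable RP2D is established, the study will proceed with an expansion cohort".
4. **DL3, as a holding rule:** two or more affected patients stop enrolment at that level.

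Full rules for opening and stopping DL3, and for one affected patient of six at DL1 or DL2, are separate matters and need their own treatment.

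The cost is four sentences reworded and two added, with no added patients, visits or procedures.

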2.5 METHOD FOR ASSIGNING SUBJECTS TO STUDY GROUPS

Subjects will be assigned to the dose-finding arm in cohorts of 3 patients until the RP2D is established (estimated 12-18 subjects). The next 15 enrolled subjects will be assigned to the expansion cohort, stage 1. The following 17 enrolled subjects will be assigned to the expansion

cohort, stage 2. Once the expansion cohort has reached a goal of 32 total patients, further enrollment will be closed. Patients will not be randomized and will be assigned to arms, cohorts and stages by the order of enrollment alone. No placebos will be used.

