3 SUBJECT SELECTION AND WITHDRAWAL

3.1 Number of Subjects

Twelve to eighteen subjects from any of the study sites are expected in the dose-finding arm, and 32 in the expansion cohort for a total of 44-50 patients.

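### The escalation rules written in section 6.2.1 do not deliver the estimated 12–18 dose-finding patients and usually fall short of it

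*Combined protocol and SAP*

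**What the plan says.** Section 6.2.1 of the combined protocol and SAP describes the design: "A 3+3 trial design with 3 dose levels and 2 optional dose de-escalation levels will be used". Patients enter in threes. DL1 without a DLT leads to DL2, and three more patients are treated at a level only when a DLT has occurred there. The RP2D is then named in one of three ways:

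- DL2 is clean: "If there are no DLTs at DL2, DL2 will be the RP2D".
- A de-escalation level is clean: "If a dose level has been lowered to DL-1 or DL-2 and no patients experience a DLT, that dose will be the RP2D".
- DL2 fails: if "two or more patients in a cohort of 3-6 patients experience dose-limiting toxicity, the RP2D will be defined as dose level 1". No patients are added at DL1 in that case, even if only three were treated there.

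A closing note in 6.2.1 lets the final choice draw on the data from every cohort. It sets no number of patients.

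Section 6.1 says the arm's size may vary with the adverse events seen, "with an estimated size of 12-18 subjects". Section 2.5 repeats that estimate, and 3.1 states: "Twelve to eighteen subjects from any of the study sites are expected in the dose-finding arm, and 32 in the expansion cohort". The synopsis and 3.1 give 44–50 patients in total. Section 6.2.2 lets dose-finding patients treated at the RP2D count towards the expansion cohort's 32.

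Table 2 (in 4.2.1.1) and the endpoint definition in 2.7 run up to DL3, but 6.2.1 contains no rule that reaches DL3. Section 1.2.2.1 hypothesises that no DLTs will be found up to the highest planned doses.

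**The concern.** The size stated for the dose-finding arm should be one that its own rules produce, at least on the path the sponsor expects. Here the rules stop much sooner, and the document does not say that the RP2D may rest on three patients.

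The RP2D is a co-primary endpoint of the dose-finding cohort and is the dose used in expansion for up to 12 cycles. The dose-finding arm is also the only place where the three-drug combination has a formal DLT window (cycle 1), because expansion patients start obinutuzumab in cycle 4. A reader of the synopsis or 3.1 would expect more evidence behind the chosen dose than 6.2.1 secures.

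**Working it through.** **Inputs from the document.** Cohorts of 3; three more at a level only after a DLT; the RP2D rules quoted above (6.2.1). Dose-finding size 12–18 (2.5, 3.1, 6.1). Expansion 32 and total 44–50 (3.1).

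**Assumptions.** The document gives no DLT rate, so four profiles for DL1/DL2/DL3 were used: 5% flat, 10% flat, 10/20/30% and 20/30/40%. DL-1 and DL-2 take the DL1 rate. One DLT in six at DL1 or DL2 has no stated action and is taken as tolerated. Section 6.2.1 conflicts with itself on 2 or 3 DLTs in the first three patients (add three, or move down), so both readings were run.

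**1. The plan's own figures.** 12 + 32 = 44 and 18 + 32 = 50, so the total reproduces. The 12 and 18 are not derived anywhere. They match three levels with six at the chosen dose (3 + 3 + 6 = 12; 6 + 6 + 6 = 18), but that is an inference.

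**2. The path without DLTs.** As written: 3 (DL1) + 3 (DL2) = 6, with 3 at the RP2D. If escalation continues to DL3: 3 + 3 + 3 = 9, with 3 at the RP2D. Neither gives 12.

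**3. Reachable totals as written.** 6, 9, 12, 15 and 18. Paths that clear DL1 give only 6, 9 or 12; totals of 15 and 18 need de-escalation.

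**4. One case by hand** (10% flat, DL2 as top, stepping down at once after 2 or 3 of 3). Per level:

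- 0/3: 0.9³ = 0.729.
- 1/3: 3 × 0.1 × 0.9² = 0.243.
- 2 or 3 of 3: 0.028.
- Cleared at six: 0.243 × 0.729 = 0.177.
- Failed at six: 0.243 × 0.271 = 0.066.

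P(n = 6) = 0.729 × 0.729 + 0.729 × 0.028 + 0.028 × 0.729 = 0.572.

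P(n = 9) = 0.729 × 0.243 + 0.177 × (0.729 + 0.028) + 0.066 × 0.729 + 0.028 × 0.177 + 0.028² × (0.729 + 0.028) = 0.365.

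P(n < 12) = 0.572 + 0.365 = 0.937.

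**5. All profiles, by the same exact enumeration.** Cells 2–5 are P(n < 12).

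| DLT rates | DL2 top, step down at 2/3 | DL2 top, always add three | Three levels, step down at 2/3 | Three levels, always add three | RP2D rests on 3 patients |
|---|---|---|---|---|---|
| 5% flat | 98% | 98% | 68% | 68% | 88% |
| 10% flat | 94% | 93% | 55% | 52% | 80% |
| 10/20/30% | 91% | 89% | 51% | 41% | 75% (74% with three levels) |
| 20/30/40% | 80% | 73% | 58% | 45% | 70% |

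**6. Information in three patients.** The one-sided 95% upper limit after no DLTs is 1 − 0.05^(1/n): 63% for n = 3 and 39% for n = 6. At a true DLT rate of 40%, a level is accepted with probability 0.6³ + (3 × 0.4 × 0.6²) × 0.6³ = 0.31 under the three-patient rule. If six are always required with at most one DLT, it is 0.6⁶ + 6 × 0.4 × 0.6⁵ = 0.23.

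**7. Effect of requiring six at the RP2D.** With DL2 as top, the path without DLTs gives 3 + 6 = 9, and P(n < 12) is still 71% at a common 10% rate and 50% at 20%. With three levels it gives 3 + 3 + 6 = 12. Early toxicity can still end the arm at 9: P(n < 12) is 5% at a common 10% rate and 14% at 20%.

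**The case against.** **The range is only an estimate.** This stands. Section 6.1 ties it to adverse events, and 12, 15 and 18 are all reachable when DLTs occur. A reader might infer that 12 is a promised minimum; the wording does not support that. What remains is that the estimate leaves out the very path hypothesised in 1.2.2.1.

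**Part of the shortfall belongs to the missing DL3 step.** This also stands. The total of 6 and the 73–98% arise because 6.2.1 ends at DL2. With three levels the figures are 9 patients without DLTs and 41–68%. The gap narrows but does not close, and the RP2D still rests on three patients about as often.

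**A 3+3 design may name a dose after 0/3.** It may. Six at the RP2D is a design choice, and nothing in the document makes it obligatory. If three is intended, though, the stated size is wrong and should change.

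**Other safeguards exist.** The closing note allows judgement. The dose-modification plan is reviewed before expansion (6.2.2), safety is discussed weekly (10.1), and the expansion can stop after 15 patients. These soften the consequence, but none adds patients to the DLT assessment, and the stop after 15 is for futility only.

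**Conclusion.** The point holds as a mismatch between the written rules and the stated size. As written, 6.2.1 ends at 6 patients with 3 at the RP2D when no DLT occurs, and falls short of 12 with probability of about 73–98% over the profiles and readings examined. With three levels the no-DLT total is 9 and the shortfall probability is 41–68%, roughly an even chance. The RP2D rests on three patients in about 70–88% of trials. The path counts follow from the text alone; the probabilities depend on the assumed DLT rates and on treating 1/6 as tolerated.

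A reader might also infer that the co-primary adverse event and discontinuation rates rest on the same three patients. The document does not say so: 2.7 lists those rates for the dose-finding cohort, and 6.3 analyses safety and tolerability in all treated patients of that cohort.

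**What to change.** Reconcile 6.2.1 with Table 2, 2.7 and the sample size, including which level is the highest to be tested. Then take one of two routes; the choice is the sponsor's.

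**(a) Keep the three-patient rule.** Restate the dose-finding size as 6–18 in 2.5, 3.1 and 6.1 (9–18 for runs that go through three levels without early toxicity). State that the RP2D may rest on three patients. Recompute the total in the synopsis and 3.1 under the carry-over in 6.2.2: the low end is 6 + 32 = 38 if RP2D patients do not count towards the 32, and 38 − 3 = 35 if they do. Simply writing 38–50 would conflict with 6.2.2. The cost is wording only.

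**(b) If 12–18 was meant to include a confirmation cohort, write it in.** State in 6.2.1 that the RP2D needs six DLT-evaluable patients with at most one DLT, including when DL1 is chosen because DL2 failed. This gives 12 without DLTs only if the DL3 step is also written; otherwise it gives 9. The cost is usually three more patients at the RP2D and about one more 28-day window. With three levels the mean total is about 13 at common DLT rates of 5–40%. A few paths, where the dose stepped back to also fails, run to 21 or 24, so the upper end of the range needs checking too.
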